Regimen consists of only oral medication using delamanid, linezolid, levofloxacin, and pyrazinamide, for nine or twelve months.

- Treatment duration

- A total of 9 months (40 weeks) when sputum culture conversion to negative occurs within three months of treatment
- A total of 12 months (52 weeks) when sputum culture conversion to negative occurs between 3 and 6 months of treatment

- Combination of treatment regimen

- Delamanid, 200mg/day (100mg bid)
 - Use for the entire treatment period unless it must be stopped for reasons such as adverse events.
- Linezolid
 - 600mg/day during the first two months
 - 300mg/day afterwards until the end of treatment

Confidential

MDR-END v14.0, 20Mar2020

- If linezolid re-administration is required after temporary discontinuation due to adverse events, the dose reduction to 300mg is allowed even within two months of treatment.
- Levofloxacin
 - $\leq 50\text{kg}$, 750mg/day
 - $>50\text{kg}$, 1000mg/day
 - Can be reduced or substituted with moxifloxacin due to reasons such as adverse events, and at this time, QT prolongation should be observed closely. Also, this substitution will not be considered as a drug change since both are fluoroquinolones of similar potency.
 - Once a day
- Pyrazinamide
 - $<50\text{kg}$, 1000mg/day
 - 50-70kg, 1500mg/day
 - $>70\text{kg}$, 2000mg/day
 - Can be reduced due to adverse event. Even if pyrazinamide resistance is discovered on the phenotypic drugs susceptibility testing after commencing treatment, it can be continued (20).
 - Once or divide in two or three

Since the definition of treatment outcomes follows the 2014 WHO Guidelines (20), as described in the ‘Research Protocol 6. Definition’, the change of a drug is allowed according to medical judgments, such as adverse drug reactions. However, the change of two or more drugs is considered ‘treatment failed’ and the participants will be withdrawn from the study.

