5.2. Primary Outcome

• Treatment success rate at 24 months after the initiation of treatment:

- ‘Cured’ and ‘treatment completed’ are defined as treatment success, and ‘culture’ defined below refers to results of liquid culture.
- Treatment failure, death, loss to follow-up, transfer out and relapse were excluded from treatment success.
- Definitions of treatment outcomes refer to 2014 WHO Guidelines (20). However, ‘stopping’ of drugs during treatment will not be considered as ‘drug change’ (Please see ‘6 Definitions’ in this protocol below.).

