8.7. Withdrawal

- 1) When the investigator judges that participating in this clinical trial would not be in the best interests of the subject
- 2) When the subject withdraws consent
- 3) Treatment failure
- 4) When the subject becomes pregnant while on anti-TB medication.
- 5) When investigators get additional test results of resistance like below,
 - a) fluoroquinolone resistance (phenotypic or molecular method)
 - b) rifampicin monoresistance is confirmed
 - c) rifampicin susceptible

* Subjects who withdrawn from the study will receive the same treatment with other TB patients by standard of care treatment.

Confidential

MDR-END v14.0, 20Mar2020

9. Checking for Developing Resistance Against Study Drug

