10.2. Statistical Analysis Method

1) Analysis Group Definition

Data obtained from subjects through clinical trials will be analyzed by mITT (Modified Intention-To-Treatment) analysis and PP (Per-Protocol) analysis. Efficacy evaluation will be based on a mITT (Modified Intention-To-Treatment) and additional analysis on PP (Per-Protocol) group. Safety analysis will be performed on the safety group.

- The mITT (Modified Intention-To-Treatment) group includes participants who are randomized after satisfying eligibility criteria and receive study drugs at least one time.
- The PP (Per-Protocol) group includes participants that satisfy the following among mITT group.
 - 1) When completing over 80% of the planned treatment (in other words, for control arm, 64 weeks or longer treatment; For investigational arm, 32 weeks or longer treatment in the 9-month treatment group and 42 weeks or longer treatment in the 12-month treatment group)
 - 2) Participants who completed the study per protocol during the clinical trial period.
- The Safety analysis group includes participants who receive study drugs at least one time.

2) Handling of Missing Data

When categorized as 'loss to follow-up', 'withdrawal', or 'withdrawal of consent', it is deemed as following.

- ① 'Treatment failure' in the case of dropping out due to 'loss to follow-up', 'investigator's decision', 'withdrawal of consent', 'treatment failure', or 'death' during the treatment
- ② 'Not accessible' in the case of dropping out due to pregnancy during the treatment
- ③ 'Treatment failure' in the case of dropping out due to 'relapse' after the treatment completion
- ④ 'Not accessible' when there is no evidence of treatment failure, such as bacteria reversion in the case of withdrawal due to 'loss to follow-up', 'investigator's decision', 'withdrawal of consent', 'pregnancy', or 'death' after the treatment completion

3) Basic Characteristics Analysis of Subjects Prior to Administration of Study Drugs

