3.1 General Principle of Result Analysis

Data obtained from subjects through clinical trial will be analyzed by mITT (modified Intention-To-Treatment) analysis and PP (Per-Protocol) analysis. Efficacy evaluation will be based on a mITT (modified Intention-To-Treatment) and additional analysis on PP (Per-Protocol) group. Safety analysis will be performed on mITT, PP and the safety group (study drug administration group).

Subject Group	Definition
mITT	
- The mITT group includes participants who are randomized after satisfying eligibility criteria and receive study drugs at least one time. The subjects are not confirmed to be additionally resistant to fluoroquinolone, mono-resistant to rifampicin, or susceptible to rifampicin.

PP	
The PP (Per-Protocol) group includes participants that satisfy the following among the mITT group.
 
When completing over 80% of the planned treatment
 
: For control arm, 64 weeks or longer treatment; For investigational arm, 32 weeks or longer treatment in the 9-month treatment group and 42 weeks or longer treatment in the 12-month treatment group

Safety	
Participants who completed the study per protocol during the clinical trial period
 
: More than 80% of the planned period before treatment is completed, the following cases are considered protocol violation and excluded from the analysis group
 
① withdrawal or death.② The sputum test before culture conversion was not conducted③ Administration of study drug in the control arm 
The Safety analysis group includes participants who have taken study drugs at least one time.
 
: Evaluation based on the administration of study drug (delamanid or linezolid)

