3.2 Handling of Missing Data

When categorized as 'loss to follow-up', 'withdrawal', or 'withdrawal of consent' will be considered as below.

- ① 'Treatment failure' in the case of dropping out due to 'loss to follow-up', 'investigator's decision', 'withdrawal of consent', 'treatment failure', or 'death' during the treatment
- ② 'Not accessible' in the case of dropping out due to 'pregnancy' during the treatment
- ③ 'Treatment failure' in the case of dropping out due to 'relapse' after the treatment completion. However, reinfection by other strain is 'not assessable'.
- ④ 'Not accessible' when there is no evidence of treatment failure, such as bacteria reversion in the case of withdrawal due to 'loss to follow-up', 'investigator's decision', 'withdrawal of consent', 'pregnancy', or 'death' after the treatment completion

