4.1 Subject Participation Status in Clinical Trial

The subject distribution can be summarized as follows as the result of the clinical trial (Figure 1 and Table 1).

[figure not shown]

Figure 1. Subject Enrollment Distribution

Table 1. Clinical Trial Results

	Investigational Arm	Control Arm
Enrollment, n	xx	xx
Non administration of study drug	xx	xx
No randomization due to screening failure	xx	xx
Violation of inclusion/exclusion criteria	xx	xx
Violation of the inclusion criterion 1	xx	xx
Violation of the inclusion criterion 2	xx	xx
Violation of the inclusion criterion 3	xx	xx
Violation of the exclusion criterion 1	xx	xx
Violation of the exclusion criterion 2	xx	xx
Violation of the exclusion criterion 3	xx	xx
Violation of the exclusion criterion 4	xx	xx
Violation of the exclusion criterion 5	xx	xx
Violation of the exclusion criterion 6	xx	xx
Violation of the exclusion criterion 7	xx	xx
Violation of the exclusion criterion 8	xx	xx
Fluoroquinolone resistance confirmed during the study	xx	xx
Rifampicin mono-resistance confirmed during the study	xx	xx
Rifampicin susceptibility confirmed during the study	xx	xx
mITT analysis group, n	xx	xx
Treatment of less than 80% throughout the planned period	xx	xx
Withdrawal or death before treatment completion (less than 80% of the planned period)	xx	xx
Investigator's judgment that participating in the study is not beneficial to the subject	xx	xx

Withdrawal of consent	xx	xx
Treatment failure	xx	xx
Pregnancy	xx	xx
Death	xx	xx
Non-execution of sputum testing before culture conversion to negative	xx	xx
Administration of study drug in the control arm	xx	xx
PP analysis group, n	xx	xx

※ Safety analysis (per the administration of study drugs)

	Investigational Arm	Control Arm	Total
Number of enrollments, n	xx	xx	xx
Non-administration of study drug	xx	xx	xx
Safety analysis (per the administration of study drugs), n	xx	xx	xx
Administration of Delamanid or linezolid	xx	xx	xx
No administration of Delamanid or linezolid	xx	xx	xx

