4.4 Adherence Assessment

Table 14 below presents the distribution of adherence to study drug of both arms at each visit and throughout the entire treatment period.

In this case, for the final adherence of each subject, the total adherence to each drug is calculated separately, and the average value is defined as the final adherence. An independent t-test or Wilcoxon rank sum test is performed only for final adherence and comparisons are made between groups.

Table 14. Adherence Assessment

			Investigational arm (N=xx)		Control arm (N=xx)	p-value	
Final Adherence	n	mean±sd	xx	xx.xx±xx.xx	xx	xx.xx±xx.xx	0.xxxx † or *
Delamanid		median [min, max]		xx.xx[xx.xx,xx.xx]		xx.xx[xx.xx,xx.xx]	
Linezolid	n	mean±sd	xx	xx.xx±xx.xx	xx	xx.xx±xx.xx	0.xxxx † or *

		median [min, max]		xx.xx[xx.xx,xx.xx]		xx.xx[xx.xx,xx.xx]	
Levofloxacin	n	mean±sd	xx	xx.xx±xx.xx	xx	xx.xx±xx.xx	0xxxx † or *
		median [min, max]		xx.xx[xx.xx,xx.xx]		xx.xx[xx.xx,xx.xx]	
Pyrazinamide	n	mean±sd	xx	xx.xx±xx.xx	xx	xx.xx±xx.xx	0xxxx † or *
		median [min, max]		xx.xx[xx.xx,xx.xx]		xx.xx[xx.xx,xx.xx]	
Other drug 1	n	mean±sd	xx	xx.xx±xx.xx	xx	xx.xx±xx.xx	0xxxx † or *
		median [min, max]		xx.xx[xx.xx,xx.xx]		xx.xx[xx.xx,xx.xx]	
Other drug 2	n	mean±sd	xx	xx.xx±xx.xx	xx	xx.xx±xx.xx	0xxxx † or *
		median [min, max]		xx.xx[xx.xx,xx.xx]		xx.xx[xx.xx,xx.xx]	
	n	mean±sd	xx	xx.xx±xx.xx	xx	xx.xx±xx.xx	0xxxx † or *
		median [min, max]		xx.xx[xx.xx,xx.xx]		xx.xx[xx.xx,xx.xx]	

† p-value by t-test

* p-value by Wilcoxon rank sum test

5. Efficacy Evaluation Results

The efficacy evaluation uses the mITT group as the main analysis group and the PP group as the auxiliary analysis group. The mITT analysis includes randomized subjects after satisfying eligibility criteria and receive study drugs at least one time. The subjects are not confirmed to be additionally resistant to fluoroquinolone, mono-resistant to rifampicin, or susceptible to rifampicin.

The PP analysis includes subjects included in the mITT group and have completed 80% or more administration through the planned treatment period has completed the clinical trial according to the study protocol during the clinical trial period.

The mITT analysis of the primary efficacy evaluation excludes the subjects judged to be "Not assessable". The subgroups according to the presence or absence of pyrazinamide resistance are additionally analyzed of the primary outcome.

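### The per-protocol set drops participants who fail or die before 80% of planned treatment, although the primary endpoint counts them as non-success

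*Combined protocol and SAP*

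**What the plan says.** **Endpoint.** Protocol 5.2: "Treatment failure, death, loss to follow-up, transfer out and relapse were excluded from treatment success". SAP 3.2 scores as treatment failure any dropout for several reasons, ending with "withdrawal of consent', 'treatment failure', or 'death' during the treatment".

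**Withdrawal.** Protocol 8.7 lists "Treatment failure" as a reason for withdrawal. Protocol 5.1.2 classes a change of two or more drugs as treatment failed, "and the participants will be withdrawn from the study".

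**PP set.** Protocol 10.2 and SAP 3.1 require more than four fifths of the plan to have been completed and state the minimum by arm: "for control arm, 64 weeks or longer treatment; For investigational arm, 32 weeks or longer treatment in the 9-month treatment group". The 12-month group has its own minimum, 42 weeks. SAP 3.1 then adds three exclusions (withdrawal or death; no sputum test before conversion; study drug in the control arm), introduced by "More than 80% of the planned period before treatment is completed, the following cases are considered protocol violation and excluded from the analysis group".

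**Table 1.** SAP 4.1 gives the first of these as "Withdrawal or death before treatment completion (less than 80% of the planned period"), with treatment failure and death among the reasons listed beneath it. SAP section 5 restates PP as participants who "have completed 80% or more administration through the planned treatment period".

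**Role of PP.** SAP section 5 makes mITT the main set and PP auxiliary. Table 15 still reports a PP difference with a lower limit, footnoted to -10%, overall and by smear status. Table 22 does the same by pyrazinamide resistance.

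**The concern.** Failing or dying on the assigned regimen is an outcome, not a departure from the protocol. Here failure leads to withdrawal, withdrawal before 80% leads to exclusion from PP, and the excluded participant would otherwise have counted as a non-success. Membership of PP therefore depends partly on the result being measured.

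In a non-inferiority trial PP is reported to show that the mITT conclusion does not come from dilution by poor adherence. A set that has lost part of its failures is a weaker check: both success rates rise and the difference between arms can move. Separately, someone programming from the SAP 3.1 sentence and someone programming from Table 1 would build different sets.

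**Working it through.** **1. The plan's own cut-offs reproduce.** Planned durations are 80 weeks for control (end-of-treatment column, protocol 7.1) and 40 or 52 weeks for the investigational arm (protocol 8.4).
- 0.8 × 80 = 64
- 0.8 × 40 = 32
- 0.8 × 52 = 41.6, rounded to 42

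This is one 80% rule applied to three durations, and there is no arithmetic error.

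**2. Where failures for non-conversion fall.** Protocol 6.4 sets the intensive phase at 6 months in the investigational arm and proposes an 8-month cut-off where no maximum is defined.
- Investigational: 6 × 52/12 = week 26
- Control, if the 8-month cut-off applies: 8 × 52/12 = about week 35

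A participant whose treatment ends then fails the duration rule alone. Allowing for the 6-week culture incubation (protocol 8.5) gives about weeks 32 and 41. The control figure is still well before 64. In the investigational arm the 9-month plan, with its 32-week cut-off, requires conversion within three months, so a six-month non-converter could only be held to 42 weeks. Protocol 5.1.2 in fact states no planned duration for participants who have not converted by six months, so 80% of their plan is undefined.

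**3. The two windows compared.**

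| On-treatment event | Table 1 (less than 80%) | SAP 3.1 read literally (more than 80%), plus duration rule |
|---|---|---|
| Failure or death before 80% | removed | removed (duration rule) |
| Failure or death after 80%, before completion | kept as non-success | removed |
| Relapse after completion | kept as non-success | kept as non-success |

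The literal reading fits badly. The same sentence governs a missed sputum test before conversion. In participants assigned 9 or 12 months, conversion falls within six months (week 26), before weeks 32 and 42, so such a test could not be missed after 80% of the plan. The duration criterion and SAP section 5 also point to Table 1.

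**4. Illustration of size.** The shares removed are assumptions; the documents give none. With true success P and a share f of non-successes removed, PP success = P / (P + (1 - f)(1 - P)). Take control 80% (the plan's figure) and investigational 70%, which puts the difference at the margin. The last column is the chance that the lower 95% limit exceeds -10 points, from 400,000 simulated trials with 51 per arm (102 × 0.50).

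| f investigational / control | PP success | Difference, points | Wald / Newcombe |
|---|---|---|---|
| 0 / 0 (no removal) | 70.0% vs 80.0% | -10.0 | 2.7% / 2.7% |
| 0.5 / 0.5 | 0.70/0.85 = 82.4% vs 0.80/0.90 = 88.9% | -6.5 | 8.2% / 6.4% |
| 0.5 / 0.3 | 82.4% vs 0.80/0.94 = 85.1% | -2.8 | about 17% / 14.5% |
| 0.3 / 0.5 | 0.70/0.91 = 76.9% vs 88.9% | -12.0 | about 1.6% / 1.4% |

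**5. Third exclusion.** SAP 3.1 calls study drug in the control arm a protocol violation. Protocol 5.1.2 allows linezolid or delamanid in controls with injectable resistance, or to strengthen the regimen after adverse reactions. The two passages conflict on the label.

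**The case against.** The strongest reply is that PP is only auxiliary: mITT decides, and there these participants count as failures. That is correct, and it limits the point to the supporting analysis. It does not remove the point, because PP has its own reported limit against the margin.

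Four stronger readings are tempting, and the documents do not support them.

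- *That the SAP sets two deliberately opposite windows.* The duration criterion, Table 1, SAP section 5 and the sputum-test exclusion all indicate a wording slip. It still needs correcting, because it stands in the section that defines the set.
- *That PP loses all on-treatment failures and deaths.* Under Table 1 those after 80% stay, as do relapses, and Table 15 keeps a treatment-failure row for PP.
- *That 64 weeks against 32 or 42 shows unequal removal by arm.* These are the same fraction of different planned durations. They do not measure how many failures each arm loses.
- *That PP is biased towards non-inferiority.* The illustration runs from -2.8 to -12.0 points according to the assumed shares, so no direction is established.

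It is also fair to say that Table 1 and SAP 3.3 already plan to show removals by reason and arm, so nothing more is needed there. Leaving out controls who received the investigational drugs is a legitimate way to keep the arms distinct. Only the violation label conflicts with the protocol.

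**Conclusion.** The point holds for participants who fail or die on assigned treatment before 80% of the planned period. This follows from the text of both documents and needs no assumption about numbers. It includes non-converters whose treatment ends with the intensive phase; for controls, that timing assumes the 8-month cut-off.

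The primary mITT conclusion is unaffected. The consequence is that the PP comparison, overall and in the smear and pyrazinamide subgroups, gives weaker support than its presentation beside mITT suggests. Its size cannot be stated from the documents. The shift from -10 to -6.5 points is an illustration that assumes half the non-successes are removed in each arm, and unequal shares could move the difference either way.

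The SAP 3.1 window is very probably a drafting error, and the control-arm label is a secondary inconsistency. All of this should be settled before the analysis sets are fixed.

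**What to change.** 1. In protocol 10.2, SAP 3.1 and Table 1, keep in PP, as non-success, participants who meet treatment failure or die on assigned treatment. Apply the 80% rule only to those who stop for other reasons. This also removes the need for a planned duration in investigational-arm non-converters who meet treatment failure.
2. Reword the SAP 3.1 sentence so that its window agrees with Table 1 and SAP section 5.
3. Reconcile the violation label in the third PP exclusion with protocol 5.1.2. The sponsor may still leave those controls out of PP, but should report the PP result with and without them.

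The cost is wording in three places, PP programming and one additional PP run; no new data are needed. The drawback is that PP success rates will look lower than under the present definition, because failures now removed will be counted.

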3.2 Handling of Missing Data

When categorized as 'loss to follow-up', 'withdrawal', or 'withdrawal of consent' will be considered as below.

- ① 'Treatment failure' in the case of dropping out due to 'loss to follow-up', 'investigator's decision', 'withdrawal of consent', 'treatment failure', or 'death' during the treatment
- ② 'Not accessible' in the case of dropping out due to 'pregnancy' during the treatment
- ③ 'Treatment failure' in the case of dropping out due to 'relapse' after the treatment completion. However, reinfection by other strain is 'not assessable'.
- ④ 'Not accessible' when there is no evidence of treatment failure, such as bacteria reversion in the case of withdrawal due to 'loss to follow-up', 'investigator's decision', 'withdrawal of consent', 'pregnancy', or 'death' after the treatment completion

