3.6.1 Primary Efficacy Evaluation

The primary outcome of this clinical trial is the treatment success rate at 24 months after the initiation of treatment (**based on the results of liquid culture**). It describes the treatment success rate of the control arm and the investigational arm with a two-sided 95% confidence interval. Then, in order to tests for non-inferiority of the investigational arm, when the lower limit of one-sided 97.5% confidence interval of the difference ($P_I - P_C$) between control and investigational arm is larger than the non-inferiority margin of -10%, it is concluded that the treatment success rate of the investigational arm is non-inferior to the treatment success rate of the control arm. The subjects whose treatment result is assessed as 'Not accessible' are excluded from the primary outcome evaluation.

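### Between investigational and control end of treatment, the same loss, withdrawal or death is excluded in one arm and a failure in the other, and no sensitivity analysis applies one rule to both

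*Combined protocol and SAP*

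**What the plan says.** The missing-data text is the same for both arms and works by treatment phase.

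- **During treatment** (SAP 3.2 item 1, same in protocol 10.2): dropping out for loss to follow-up, investigator's decision, withdrawal of consent, treatment failure "or 'death' during the treatment" is scored as failure.
- **After treatment completion** (SAP 3.2 item 4): the patient is "Not accessible' when there is no evidence of treatment failure, such as bacteria reversion in the case of withdrawal due to 'loss to follow-up", and likewise for investigator's decision, consent withdrawal, pregnancy or death. Protocol 10.2 has the same rule: "Not accessible' when there is no evidence of treatment failure, such as bacteria reversion in the case of withdrawal".
- **Consequence** (SAP 3.6.1): "The subjects whose treatment result is assessed as 'Not accessible' are excluded from the primary outcome evaluation".

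Treatment length differs by arm. Protocol 8.4 ends investigational treatment at week 40 or 52. Protocol 5.1.2 recommends 20 to 24 months for control, and the control schedule in protocol 7.1 places end of treatment from week 80. The per-protocol (PP) threshold, "For control arm, 64 weeks or longer treatment", taken as 80% of the plan, also gives 64/0.80 = 80 weeks. The endpoint is read at 24 months in both arms.

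The other efficacy analyses are PP, sputum smear strata and pyrazinamide-resistance subgroups. SAP Tables 15 and 22 carry the same exclusion into all of them.

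**The concern.** Take two patients, one per arm, both doing well and both lost in month 15 without evidence of failure. The investigational patient has finished treatment and leaves numerator and denominator. The control patient is still on treatment and is a failure. The rule is neutral in wording, but its effect depends on the arm because treatment length does. After control treatment ends, both arms are scored alike, so the issue is confined to that window.

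With about 51 evaluable patients per arm, one patient is worth about 2 points (1/51) against a 10-point margin. A handful of late events can therefore decide the non-inferiority conclusion through the scoring rule alone. The plan does not test the conclusion under a rule that treats the same event at the same time alike.

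**Working it through.** **Inputs from the documents.** Success 80% (control) and 90% (investigational), margin -10 points, one-sided 2.5%, 80% power, 48 evaluable and 102 enrolled per arm, 50% fluoroquinolone-susceptible, 5% lost to follow-up (protocol 10.1, SAP 2.3.1). End of treatment as given above.

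**The plan's own figure.** The unpooled normal formula gives (1.960 + 0.842)² × (0.16 + 0.09)/0.20² = 49.06, so 50 per arm, within 2 of the stated 48. Inflation: 48/(0.50 × 0.95) = 101.05, so 102, as stated. Before losses, 102 × 0.50 = 51 per arm are evaluable; I use 51.

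**Assumptions of mine.** Loss, withdrawal and death together have rate L, equal in both arms and spread evenly over 104 weeks. L = 5% uses the plan's loss figure; L = 10% is only illustrative. Control treatment T_C is 80 to 104 weeks, investigational T_T is 40 or 52. Intervals are Wald, since the SAP names no method.

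**Patients in the window.** Share = (T_C - T_T)/104, from 28/104 = 27% to 64/104 = 62%. At L = 5%: 51 × 0.05 × 0.27 = 0.7 to 51 × 0.05 × 0.62 = 1.6 patients per arm. At L = 10%: 1.4 to 3.1.

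**Shift in the difference with equal arms at 80%.** The excluded share in an arm is e = L(104 - T)/104.

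- Reference *not success in both arms*: 0.8/(1 - e_T) - 0.8/(1 - e_C). For 80/52 weeks at 5%, e_T = 0.0250 and e_C = 0.0115, giving 0.8205 - 0.8093 = +1.1 points. For 104/40 weeks, e_T = 0.0308 and e_C = 0, giving 0.8254 - 0.8000 = +2.5 points.
- Reference *lost completers are true successes*: (0.8 - e_T)/(1 - e_T) - (0.8 - e_C)/(1 - e_C), giving -0.3 to -0.6 points.

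**One-sided error at the margin.** This is an exact enumeration of excluded and success counts, 51 per arm, with true rates of 80% (control) and 70% (investigational) on the scale of each reference. Without such events it is 2.7%.

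| Reference | L = 5% | L = 10% |
|---|---|---|
| Not success in both arms | 3.4-4.8% | 4.5-8.4% |
| Excluded in both arms over the same window | 3.6-4.9% | 4.7-8.3% |
| Lost completers kept as successes | 2.1-2.3% | 1.6-2.0% |

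**Example.** One loss per arm at month 15 (15 × 52/12 = week 65), no evidence of failure. Lower limit = difference - 1.96 × standard error.

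| Rule | Investigational vs control | Difference (points) | Lower limit (points) |
|---|---|---|---|
| Planned | 43/50 vs 41/51 | +5.61 | -8.93 |
| Not success in both | 43/51 vs 41/51 | +3.92 | -10.86 |
| Excluded in both | 43/50 vs 41/50 | +4.00 | -10.35 |
| Completer kept as success | 44/51 vs 41/51 | +5.88 | -8.54 |

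Two rules meet the margin and two do not. Newcombe limits (-9.3, -11.1, -10.7, -8.9) give the same decisions. The counts were chosen near the margin: they show that a reversal is possible, not how likely it is.

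**Does PP settle it?** That depends on the wording. Protocol 10.2 requires "Participants who completed the study per protocol during the clinical trial period". SAP 3.1 says "More than 80% of the planned period before treatment is completed, the following cases are considered protocol violation and excluded from the analysis group" and lists withdrawal or death. Both can be read to remove on-treatment withdrawals and deaths in both arms. SAP Table 1 instead removes "Withdrawal or death before treatment completion (less than 80% of the planned period"), which leaves control events from week 64 to end of treatment as failures. If all other patients stay in PP, the example gives -10.35 on the first reading and -8.93 on the second.

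**The case against.** **The two events are not the same.** A control patient lost at week 65 has interrupted treatment, which protocol 6.4 defines as lost to follow-up; the investigational patient has completed the course. Protocol 2.1 names premature stopping as the main reason for treatment failure, and the shorter regimen is meant to address it. Scoring control default as failure is thus a defensible strategy choice. This stands, and it is why the primary rule can stay. It does not replace a check under one rule.

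**Direction and size are uncertain.** This stands too. A reader might infer that the rule is biased towards the investigational regimen. The documents do not support that: the sign reverses if lost completers are true successes, post-treatment follow-up visits for relapse exist only in the investigational arm (protocol 8.4.2) and work against it, and loss rates by phase are not given. The 10% figures have no source in the plan.

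**Table 15 already shows the counts.** It gives mITT, not-assessable, success and failure counts by arm. The not-success and kept-as-success versions can largely be worked out from them, though pregnancy and reinfection are also not assessable. So it would go too far to say that a reader cannot probe the result. The common-window exclusion cannot be recovered, and an analysis chosen after the results of an open-label trial carries less weight than a prespecified one.

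**Completers later lost or dead.** One might read protocol 5.2, which lists death and loss among outcomes that are not success, as contradicting protocol 10.2. That is not established. Protocol 10.2 and SAP 3.2 agree on a specific rule, being left out of success is compatible with leaving the evaluation, and 6.4 ties death and loss to treatment and has a not-evaluated category. A cross-reference is enough.

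**Conclusion.** The arm-dependent scoring follows directly from the text, without assumptions, and no planned analysis applies one rule to both arms. Its consequence is modest at the plan's 5% loss but can matter with 51 per arm. Relative to not success in both arms, the error is up to about 1.8 times its base value (4.8% against 2.7%); relative to kept-as-success it is slightly below base. These figures rest on equal, evenly spread losses, Wald limits and control treatment of 80 to 104 weeks. The net bias cannot be computed from the documents. The point is therefore a missing robustness check that should be added, not a finding that the primary analysis is invalid or must be replaced.

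**What to change.** In SAP 3.2, 3.6.1 and Table 15, and in protocol 10.2, prespecify two mITT sensitivity analyses of the primary endpoint, each with one rule by time since treatment start for both arms:

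- **(a)** any loss, withdrawal, transfer or death before month 24 is not success;
- **(b)** such events without evidence of failure are excluded in both arms from one fixed week to month 24, the same for all patients. Week 52, the latest planned investigational end of treatment, is an example. The rule should also state a common score for events before that week, such as not success.

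Describe non-inferiority as robust only if it holds under (a) and (b). Keeping lost completers as successes may be reported as a separate scenario. It depends on treatment completion, so it should not be presented as a uniform rule: in the example it scores one loss as success and the other as failure.

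Report not-assessable counts by arm and reason. Cross-reference protocol 5.2 and 6.4 to the scoring of completers later lost or dead. Reconcile the PP wording in protocol 10.2, SAP 3.1 and SAP Table 1; the SAP 3.1 phrase may only be a slip.

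The cost is wording and a few table rows from data already planned. The downside is a possibly less favourable result, since (a) also counts some patients who completed treatment as not success.
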